Screening: Once consents have been signed, the patients will be assessed by the MD for participation and screened to confirm they meet inclusion and exclusion criteria.

The screening will take approximately 20 minutes, not including routine care.

Pre-treatment (Visit 0): This visit will follow the screening visit. The following materials will be given and tests will be administered:

- a) demographic and history survey
- b) 24 hour voiding diary
- c) visual analog scale (VAS) for bladder pain
- d) Pelvic Pain and Urgency/Frequency Patient Symptom Scale (PUF Questionnaire)
- e) O'Leary-Sant IC Symptom and Problem Index
- f) urine pregnancy test (for all premenopausal subjects)

Questionnaires will be provided and will take 20 minutes to complete. The 24 hour voiding diary will be sent home with the patient and will require approximately 20 minutes spread throughout 1 day.

Treatment (Visits 1-5): Prior to the start of first treatment visit, the subject will return the above forms/questionnaires. These visits will be conducted in the UCI urogynecology clinic. PTNS will be administered by a clinical nurse under physician supervision. This is standard of care in clinical practice. These treatments will occur weekly for 12 weeks total. Treatments will be administered per standard protocol. At all visits, the nurse will inquire regarding any noted adverse reactions to treatment and will have the subject complete a VAS.

Each treatment takes approximately 30 minutes.

Treatment (Visits 6): This treatment visit will be administered in the same fashion and with the same requirements as all other treatment visits. Following this visit, the subject will be provided with the following forms/questionnaires to complete prior to the subsequent visit:

- a) 7-point global response assessment (GRA) scale
- b) 24 hour voiding diary
- c) visual analog scale (VAS) for bladder pain
- d) Pelvic Pain and Urgency/Frequency Patient Symptom Scale (PUF Questionnaire)

e) O'Leary-Sant IC Symptom and Problem Index

The time required for the treatment session and completion of the forms is 45 minutes.

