Treatment (Visits 7-11): Prior to the start of seventh treatment visit, the subject will return the additional forms/questionnaires. These visits will continue to be conducted in the UCI urogynecology clinic. PTNS will be administered by a clinical nurse under physician supervision. This is standard of care in clinical practice. Treatments will be administered per standard protocol. At all visits, the nurse will inquire regarding any noted adverse reactions to treatment and will have the subject complete a VAS.

Each treatment takes approximately 30 minutes.

Final Treatment (Visit 12): This visit will be conducted per the routine protocol in visits 1-11, with any adverse reactions noted and a VAS collected. After completion of the visit, the patient will be given the following materials for completion within the subsequent two weeks.

a) 7-point global response assessment (GRA) scale

b) 24 hour voiding diary

c) visual analog scale (VAS) for bladder pain

d) Pelvic Pain and Urgency/Frequency Patient Symptom Scale (PUF Questionnaire)

e) O'Leary-Sant IC Symptom and Problem Index

The time required for the treatment session and completion of the forms is 45 minutes.

Follow-up (Visit 13): This visit will consist of a follow-up clinic visit with the subjects' provider per routine care. If not returned previously, the patient will submit the materials completed after Visit 12. The subject and her provider will review her current symptoms and complaints and create an individualized management plan. At this time, depending on their current symptoms and response to the treatment, the subjects will be offered to continue with PTNS treatments at a standard maintenance interval (typically every 4-6 weeks) or to pursue alternative care outside of the study protocol if no benefit was obtained from treatment. Any additional treatments (PTNS or otherwise) after the 12 sessions of PTNS are not considered part of the study and will be determined by provider and patient per clinical standard of care. At this time, we will offer patients to enroll in post-study follow up. If they choose to continue, they will have a visit 14.

This visit will require 30 minutes.

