This is a pilot study with primary aim to estimate the proportion of patients experiencing moderate or marked improvement in overall symptom score as measured by response to a 7-point global response assessment scale collected after the intervention period. Responders will be defined as those reporting a moderate or marked improvement in symptoms in global response score. We will estimate the proportion of responders with 95% confidence limits, as defined by a response of moderate or marked improvement on the GRA scale collected at follow-up. Pain response will be measured using the Pelvic Pain and Urgency/Frequency Patient Symptom Scale (score total range: 0-35). We will estimate mean (plus standard deviations and 95% CI) for pain score at baseline and follow-up and change in response to therapy, testing for change over time using a paired t-test.

Other secondary outcomes that we will be reviewing are: change in frequency of urinary collected in 24 hour voiding diaries, change in visual analog scale, and change in O'Leary-Sant IC Symptom and Problem Index. These data consist of continuous variables to be described using means, SDs and confidence intervals at baseline and follow-up. Change over time will also be estimated and tested for difference from zero using a paired t-test.

SECTION 4: SUBJECTS (PERSONS/CHARTS/RECORDS/SPECIMENS)

A. Number of Subjects (Charts/Records/Biospecimens)

- Indicate the **maximum number of subjects to be recruited/consented** on this UCI protocol. This is the number of potential subjects you may need to recruit to obtain your target sample size. This number should include projected **screen failures and early withdrawals**. *Note: The IRB considers individuals who sign the consent form to be "enrolled" in the research.*
- For **Mail/Internet surveys** include the number of people directly solicited.
- If the study involves use of **existing charts, records, biospecimens**, specify the maximum number that will be reviewed/tested to compile the data or the sample population necessary to address the research question.

32

- Of the maximum number of subjects listed above, indicate the **target sample size** for the study. This is the number of subjects expected to complete the study or the number necessary to address the research question.

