While subjects will be restricted from receiving new additional standard therapies during the course of the study, there is very limited risk associated with this because they will only be restricted during the course of the study protocol. Patients will be permitted to continue standard of care oral medical therapies (such as pyridium, Elmiron, or other medications considered second line in the AUA guidelines for treatment of IC/PBS) if they had been receiving this medication prior to enrollment in the trial protocol. If they so choose, they will be able to receive any other additional indicated treatments immediately following conclusion of the trial protocol. If they choose to withdraw from the study in order to receive another indicated (standard) therapy that will be noted and included in our results. Any subject who withdraws will be offered an appointment with her physician.

PHI will be collected as part of this study. Breach of confidentiality is a theoretical risk.

5. Discuss what steps have been taken and/or will be taken to **prevent and minimize** any risks/ potential discomforts to subjects (address physical risks as well as other risks such as the potential for a breach of confidentiality). Examples include: designing the study to make use of procedures involving less risk when appropriate; minimizing study procedures by taking advantage of clinical procedures conducted on the subjects; mitigating risks by planning special monitoring or conducting supportive inventions for the study.

All subjects will be carefully monitored throughout the study protocol. They will have weekly visits with a trained, urogynecology practitioner who will be administering the PTNS treatments. This provider is qualified to assess and triage complaints related to the PTNS procedure and will contact the appropriate research physician if additional assessment is indicated. The practitioner administering the PTNS treatments will work with the subject, in the standard fashion for PTNS, to minimize any transient discomfort during the treatments.

Subjects may return to UCIMC urogynecology clinic for additional visits outside of the study protocol at their own discretion, if there are any complaints they feel need to be assessed by a physician. We will work to minimize inconvenience associated with study participation by allowing the subject to schedule the PTNS treatments at the time most convenient for them, within clinic scheduling ability.

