We will prevent any possible risks to the subjects from breach of confidentiality through the methods outlined in Section 12.

C. Potential Benefits

1. Discuss the potential benefits that may accrue **directly to subjects**. **Note: Compensation is not a benefit. Do not include it in this section.**

There is no direct benefit anticipated for the subjects.

OR

There is no guarantee to subjects that they will benefit directly from participating in this study and all subjects will be informed of this during the consent process. The subject may experience an improvement in her IC/PBS symptoms because of the treatment intervention with PTNS. If the subject does experience improvement in symptoms, they may derive direct benefit by avoiding other, more invasive interventions for the treatment of this condition.

If the subject completes 12 treatment visits and returns the subsequent 24 hour voiding diary and questionnaires, they will receive a \$50 check as a stipend.

2. Describe the **potential societal/scientific benefit(s) that may be expected from this study.**

Information obtained from this study will benefit the urogynecologic, urologic and medical communities in determining if additional studies investigating the use of PTNS for the treatment of symptoms related to IC/PBS is useful. If the study intervention is found to be efficacious, this could be a significant contribution to the management of this chronic disease. If the study intervention is not found to reduce symptoms, additional information about the pathophysiology of the disease and the mechanism of action of both PTNS and SNM may be obtained. This will also allow for future research to be better directed elsewhere.

D. Risk/Benefit Assessment

Explain why the study risks are reasonable in relation to the **potential benefits** to subjects and society.

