1. If subjects will be compensated for their participation, explain **the method/terms of payment** (e.g., money; check; extra credit; gift certificate).
2. Describe the **schedule and amounts of compensation** (e.g., at end of study; after each session/visit) including the total amount subjects can receive for completing the study.
3. Specify whether subjects will be **reimbursed for out-of pocket expenses**. If so, describe any requirements for reimbursement (e.g., receipt).

Note: Compensation should be offered on a prorated basis when the research involves multiple sessions.

Not applicable - This study involves no interaction/intervention with research subjects (i.e., involves the use of records, charts, biospecimens).

No compensation will be provided to subjects.

No reimbursement will be provided to subjects.

OR

If the subject completes 12 treatment visits and returns the subsequent 24 hour voiding diary and questionnaires, they will receive a \$50 stipend (cash or gift card). No other compensation or stipends will be provided for in the study.

SECTION 12: CONFIDENTIALITY OF RESEARCH DATA

1. Indicate all identifiers that may be included in the research records for the study. Check all that apply:

Note: If this information is being derived from a medical record; added to a medical record; created or collected as part of health care, or used to make health care decisions it qualifies as PHI under HIPAA. The subject's HIPAA Research Authorization is required or a waiver of HIPAA Authorization must be requested (Appendix T).

No subject identifiers are obtained (i.e., researchers will not collect information that can link the subjects to their data)

OR

| | | |
|---|--|--|
|  Names |  Social Security Numbers |  Device identifiers/Serial numbers |
|  Dates* |  Medical record numbers |  Web URLs |
|  Postal address |  Health plan numbers |  IP address numbers |
|  Phone numbers |  Account numbers |  Biometric identifiers |
|  Fax numbers |  License/Certificate numbers |  Facial Photos/Images |

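### The end-of-treatment GRA is scheduled, and the stipend paid, only for women who complete all 12 sessions, so the plan has no route to the primary outcome in women who stop early

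*Combined protocol and SAP*

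**What the plan says.** **Primary outcome.** Section 3B estimates the proportion of responders with 95% confidence limits, "as defined by a response of moderate or marked improvement on the GRA scale collected at follow-up". It names no analysis population, no rule for a missing GRA, and no rule for women who withdraw.

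**When the GRA is collected.** In Section 3 the end-of-treatment GRA is issued at Visit 12: "After completion of the visit, the patient will be given the following materials for completion within the subsequent two weeks". Visit 13 is a second chance to hand in those same forms. An interim GRA is issued after Visit 6: "Following this visit, the subject will be provided with the following forms/questionnaires to complete prior to the subsequent visit". Neither the visit descriptions nor the visit table contains an early-termination assessment.

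**Payment.** Sections 7C and 11 set the same condition: "If the subject completes 12 treatment visits and returns the subsequent 24 hour voiding diary and questionnaires, they will receive a" $50 stipend. Section 11 adds: "No other compensation or stipends will be provided for in the study". The form's own note in Section 11 reads: "Compensation should be offered on a prorated basis when the research involves multiple sessions".

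**Withdrawal.** Section 7B bars new additional standard therapies during the study and foresees women leaving to receive one. It says such withdrawals will be recorded and reflected in the results, without saying how they enter the primary proportion. It then says: "Any subject who withdraws will be offered an appointment with her physician". No outcome form is attached to that appointment.

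**The concern.** In a single-arm study the result is one proportion, so it matters who is in the denominator. Followed as written, the plan yields an end-of-treatment GRA only from women who attend all 12 weekly sessions. The stipend reinforces this, because it gives an early stopper nothing for returning outcome forms.

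Section 7B itself names an exit route that is plausibly related to outcome: leaving to try something else. If women who leave that way are mostly non-responders and drop out of the denominator, the reported proportion is too high. Section 4A says that a true rate of at least 40% would be clinically important, and its worked example has a lower limit of 40%. The example has little room for upward bias before that reading fails.

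**Working it through.** **Inputs.** From Section 4A: target 24, maximum 32, precision ±0.2, example rate 60%, and an allowance of 33.3% for exclusion or withdrawal combined. The gap is 32 − 24 = 8 women, which is 8/24 = 33.3% of the target and 8/32 = 25% of those enrolled. The documents do not give the split of the 8 between screen failures and treated withdrawals, or the response rate among women lost. Both are varied below.

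**The plan's own figure.** Half-width = 1.96 × √(0.6 × 0.4 / 24) = 1.96 × 0.100 = 0.196, or 40.4% to 79.6%. The stated ±0.2 is reproduced.

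**Bounds on the primary proportion.** 60% of 24 is 14.4, so take 14 responders among 24 completers: 14/24 = 58.3%. With m treated women lost, the proportion among all treated women lies between 14/(24 + m), if none of them responded, and (14 + m)/(24 + m), if all did.

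| Treated women lost (m) | All lost are non-responders | All lost are responders | Shift from 58.3% |
|---|---|---|---|
| 8 (extreme: no screen failures) | 14/32 = 43.8% | 22/32 = 68.8% | −14.6 / +10.4 points |
| 4 | 14/28 = 50.0% | 18/28 = 64.3% | −8.3 / +6.0 points |
| 2 | 14/26 = 53.8% | 16/26 = 61.5% | −4.5 / +3.2 points |

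**Upward bias of a completers-only 60%.** Bias = 0.60 − [0.60 × (1 − d) + r × d], where d is the fraction of treated women lost and r is their response rate (assumed).

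| d | r = 0% | r = 20% | r = 40% | r = 60% |
|---|---|---|---|---|
| 10% | 6 points | 4 | 2 | 0 |
| 25% | 15 points | 10 | 5 | 0 |

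**Effect on the 40% reading, at the extreme.** With 14.4 expected responders out of 32 the proportion is 45%. The half-width is 1.96 × √(0.45 × 0.55 / 32) = 0.172, giving 28% to 62%. The lower limit is then well below 40%.

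**What each rule does to a woman who stops.** If she stops before session 6, she has been issued no GRA. If she stops at session 7, she has been issued the interim GRA, due back before that visit, but not the end-of-treatment one. In neither case does the schedule bring her to the form that Section 3B analyses, whatever she is paid. The stipend matters only once the form is offered to her.

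**The case against.** A reader might go further and infer that the stipend itself causes the outcome to be lost selectively. The documents do not support that, for these reasons:

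- **Mechanism.** A woman who stops before Visit 12 is never handed the end-of-treatment GRA, so prorating the payment alone would recover nothing. The visit schedule is the main cause and the stipend contributes. Among women who reach Visit 12, the payment encourages return whether or not they improved.
- **Evidence.** Nothing in the documents gives return rates, links stopping to poor response, or shows that $50 changes behaviour. Selective loss is a plausible risk only.
- **Interim data.** It would be wrong to say that early stoppers are never asked for a GRA. Women who reach Visit 6 are, and a pain VAS is taken at every treatment visit.
- **Withdrawals.** Section 7B says that withdrawals to another therapy will appear in the results. This is relevant, but it neither defines the calculation nor covers other reasons for stopping.
- **Size.** Consent comes before screening and the maximum of 32 includes screen failures. Those women receive no PTNS and do not belong in a responder denominator, so 8 is a ceiling. It is also tempting to say that the 25-point spread (44% to 69%) exceeds the ±20-point precision, but that sets a full range against a half-width. The shifts of 15 points down and 10 up are both smaller than 20.
- **Prorating note.** It is form guidance on payment and says nothing about retaining outcomes. The departure from it is real but is not evidence of bias.

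All of this limits the claim. It leaves standing that an early stopper has no scheduled end-of-treatment GRA, no payment for one, and no analysis rule to cover the gap.

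**Conclusion.** The point holds as a gap in outcome collection, made worse by an all-or-nothing stipend that departs from the form's own prorating note. It is a cheap improvement and not a fatal flaw. The possible upward shift in a completers-only proportion is at most about 15 points, if all 8 allowed losses were treated women and none responded. It is about 8 points if 4 were treated, and nil if those lost responded at the completers' rate. The direction rests on the assumption that early stoppers respond less often. Section 7B makes that plausible, but the documents do not demonstrate it.

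**What to change.** 1. **Section 3 (visit descriptions and table) and Section 7B:** state that any treated woman who stops early is asked at discontinuation for the GRA, VAS, PUF and O'Leary-Sant, either at the physician appointment already offered or by phone, which Section 3 already permits for follow-up. Record how many sessions she had received, since her GRA refers to an earlier time than Visit 12.
2. **Section 3B:** define the primary proportion over all treated women, including those assessed at discontinuation. State how a GRA that is still missing is counted (for example as non-response, with the opposite bound shown) and whether the Visit 6 GRA may stand in. Report the completers-only figure as a sensitivity analysis.
3. **Sections 7C and 11:** pay the stipend, or a fixed part of it, for returning these forms regardless of sessions completed. Reconcile the form of payment at the same time: Section 7C says a check, Section 11 cash or a gift card.

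**Cost.** At most 8 × $50 = $400, a change to the consent wording, and a short form or call for each woman who stops. The reported response rate may be lower than among completers alone. Each GRA recovered narrows the extreme range by 1/32, about 3 points.
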